#### 8.2.3. Demographic and Baseline Characteristics

Demographic data and baseline characteristics will be presented by treatment group as well as by region (US vs. Non-US). All variables will be summarized by descriptive statistics for the SAF.

The following demographic and baseline characteristics will be summarized:

Data collected at  (screening):

- Age (years): 18-34, 35-49 - calculated relative to date of consent
- Sex: Female
- Race (where participants can contribute to multiple race categories, not collected for

France)

- Ethnicity (not collected for France)
- Weight
- Height
- Body Mass Index (BMI) [kg/m^2]

Data collected during the full Baseline Cycle / Run-in:

- Mean DYS pelvic pain score
- Mean NMPP score
- Mean OPP score
- OPP score severity (4 ≤ mean < 8 moderate; mean ≥ 8 severe)
- Daily rescue medication use (% of days in cycle and mean number of tablets per day)
- Mean Dyspareunia score

#### 8.2.4. Medical, Endometriosis Surgical, Gynecological and Obstetric History

General medical history, endometriosis surgical history and gynaecological history at **CC** will be presented for the Safety Analysis Set. The data will be summarized by treatment group as detailed in sections 8.2.4.1, 8.2.4.2, and will be listed by participant.

##### 8.2.4.1. GENERAL MEDICAL HISTORY

Medical History will be coded using Medical Dictionary for Regulatory Activities (MedDRA) version 25.1 or higher.

- Medical History conditions are defined as relative medical conditions which are reported at screening prior to start of treatment and may or may not be ongoing as of the screening visit.
- Medical history conditions will be presented by System Organ Class (SOC) and Preferred Term (PT), with SOC in alphabetical order and PT in order of decreasing frequency.

##### 8.2.4.2. ENDOMETRIOSIS SURGICAL HISTORY

Summaries of endometriosis surgical history data will include the number and percentage of study participants by treatment group for the following:

- Surgical Diagnosis Method (Laparoscopy/Laparotomy)
- Years of Surgical Diagnosis of Endometriosis (<5 years, ≥5 years) - calculated relative to date of consent

#### 8.2.4.3. GYNECOLOGICAL AND OBSTETRIC HISTORY

Gynecological history data will be summarized by treatment group for the following:

- Age of Menarche (years)
- Typical Cycle Length (days)
- Usual Duration of Flow (days)
- Usual Volume of Flow (Low/Moderate/Heavy)
- Presence of Clots during Flow (Yes/No)

Summaries of pregnancy history will include the number and percentage of study participants with previous pregnancies as well as descriptive statistics for the overall number of previous pregnancies (gravidity number), number of live births and the number of times the participant has given birth to a fetus with gestational age of 24 weeks or more (parity number).

- Number of Previous Pregnancies
- Gravidity
- Number of Live Births
- Parity

#### 8.2.5. Prior, Concomitant, and Post-Treatment Medications

Medications entered in the Medical History form of the eCRF will be presented for the Safety Analysis Set and coded using WHO-Drug dictionary, September 2022 or later. In the case where it is not possible to define a medication as prior, concomitant, or post-treatment, the medication will be classified by the worst case, i.e., concomitant.

- ‘Prior’ medications are defined as any medications started prior to the day of the first dose of randomized study treatment.
- ‘Concomitant’ medications are defined as any medications taken on the day of or after the first dose of randomized study treatment and before or on the day of last

dose of randomized study treatment.

- 'Post-Treatment' medications are defined as any medications started after the day of last dose of randomized study treatment

Prior, concomitant, and post-treatment medication use will be summarized separately by preferred name using frequencies and percentages. Medications will be sorted alphabetically by Anatomical Therapeutic Chemical (ATC) Level 3 and preferred name in summaries.

Participants with multiple occurrences of a medication in the same ATC Level 3 or preferred name will only be counted once within the PT for each summary. If a medication is unable to be categorized to ATC Level 3, the most detailed level available will be used. The type of medication (Prior/Concomitant) will be indicated in the listing of all medications.

The use of prohibited pain medication registered in the eDiary will be summarized by treatment and treatment cycle for the MFAS. All use of prohibited pain medication will be listed in detail.

Use of supplied rescue medication for management of endometriosis related pain, that was reported in the eDiary as an efficacy endpoint, will not be included in the summaries and listings described above.

#### **8.2.6. Study Treatment Exposure and Compliance**

##### **8.2.6.1. STUDY TREATMENT EXPOSURE**

Exposure to randomized study treatment in days will be presented for the Safety Analysis Set.

The date of first randomized study treatment administration will be defined as the date of the randomization visit. The date of last randomized study treatment will be taken from the eCRF End of Study Treatment form.

Interruptions and lack of compliance will not be taken into account for duration of exposure.

The number and percentage of participants with exposure to randomized treatment will be summarized by treatment group for the following categories:

- <4 weeks

- 4-<8 weeks
- 8-<12 weeks
- ≥12 weeks

Duration of exposure (days) = (date of last randomized study treatment administration – date of first randomized study treatment administration) + 1.

#### 8.2.6.2. STUDY TREATMENT COMPLIANCE

Compliance with the use of study treatment overall will be presented for the SAF. Number of tablets dispensed and number of tablets returned will be taken from the eCRF Drug Accountability form. Non-compliance is defined as compliance to study treatment <75%. Non-compliance to study treatment will be summarized overall using descriptive statistics by treatment group.

Compliance (%) with randomized study treatment will be calculated based on drug accountability data as the total number of tablets taken (total dispensed – total returned) divided by the total expected number of tablets (number of tablets should be taken per day times duration of exposure) expressed as a percentage, see calculation below.

$$100 \times \frac{\sum(\text{\#tablets dispensed} - \text{\#tablets returned})}{\text{\#tablets that should be taken per day} \times \text{duration of exposure}}$$

Where # of tablets that should be taken per day is 6 tablets (1 tablet from Bottle A BID and 2 tablets from Bottle B BID), and duration of exposure (days) = date of last randomized study treatment administration – date of first randomized study treatment administration + 1.

For participants where bottles were not returned or lost, compliance will not be calculated but set to missing.

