6.4 Study Treatment Compliance

The prescribed dosage and mode of administration may not be changed. Any deviations from the intended regimen must be recorded in the eCRF.

A record of the quantity of tablets administered by each participant must be maintained and reconciled with study treatment and compliance records.

All study treatment will be administered by the study site staff when the participant is at the site. Any non-compliance will be recorded in the eCRF. Non-compliance is defined as taking any dose (more or less) other than the protocol dose.

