## **6.5. Per-Protocol Analysis Set (PP)**

The Per-Protocol analysis set is defined as a subset of all participants in the MFAS with the following exclusions.

The PP analysis set will exclude participants that either:

- Had critical or major protocol deviation with major impact on the primary endpoint.
- Were non-compliant with randomized treatment, i.e. used <75% of the protocol dose of randomized study treatment (only participants for which compliance could be calculated from randomization to last dose of treatment, and for which this compliance was <75%, will be excluded).

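### The SAP flags non-compliance only below 75%, although protocol 6.4 defines it in both directions, so tablet counts well above 100% are never tabulated as non-compliant or removed by the Per-Protocol compliance criterion

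*SAP*

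**What the plan says.** Protocol 6.4 is two-sided: "Non-compliance is defined as taking any dose (more or less) other than the protocol dose". It also requires documentation: "Any deviations from the intended regimen must be recorded in the eCRF". Protocol 6.7 treats any dose above the assigned one as an overdose.

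SAP 8.2.6.2 calculates compliance from drug accountability as tablets dispensed minus tablets returned, divided by tablets expected over the exposure period. The daily expectation is fixed: "Where # of tablets that should be taken per day is 6 tablets (1 tablet from Bottle A BID and 2 tablets from Bottle B BID". The classification then has a lower limit only: "Non-compliance is defined as compliance to study treatment <75" (percent). Incomplete returns have their own rule: "For participants where bottles were not returned or lost, compliance will not be calculated but set to missing".

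SAP 6.5 removes participants from the PP set by two routes. One is compliance: "Were non-compliant with randomized treatment, i.e. used <75% of the protocol dose of randomized study treatment", restricted to women whose compliance can be calculated. The other is deviations: "Had critical or major protocol deviation with major impact on the primary endpoint". The PP definition in protocol 9.2 has no compliance threshold. SAP Section 10 states that nothing changed from the protocol's planned analyses, apart from adding the estimand.

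**The concern.** The protocol says that excess dosing is non-compliance, and the SAP's rule cannot register it. Two outputs depend on that rule. The first is the summary of non-compliance by treatment group, which will show under-use only. The second is the PP set, whose compliance criterion takes out women who used too few tablets and has nothing to say about women whose counts show too many.

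Among the three sensitivity analyses in SAP 8.3.6, the PP repeat is the only one that bears on adherence to study treatment; the others deal with sparse diary data and with days on prohibited pain medication. In a study with three dose levels, a reader will take the PP set to be women who took roughly what they were assigned. With a one-sided limit, the compliance criterion secures only half of that.

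**Working it through.** **The plan's own figure.** The documents give no figure for compliance. The one design figure, 84% power in SAP 4.3, does reproduce. With 95 × 0.9 = 85.5 per group, difference 1 and SD 2.2, 1 / (2.2 × √(2/85.5)) = 2.97. Subtracting 1.96 leaves 1.01, which is 84.4% power by the normal approximation (84.0% by noncentral t). The present point does not depend on it.

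**Inputs.** 6 tablets per day and the 75% limit (SAP 8.2.6.2); the two-sided definition (protocol 6.4). Exposure is an assumption, because the maximum treatment duration is redacted. I use 84 days as the example (12 weeks, the start of the top exposure category in SAP 8.2.6.1) and repeat the check at 56, 90 and 100 days.

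**Formula.** Compliance (%) = 100 × (dispensed − returned) / (6 × days). At 84 days, expected = 6 × 84 = 504 tablets, and the SAP flags counts below 0.75 × 504 = 378.

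| Days (assumed) | Expected tablets | SAP flags counts below | Count at 110% | at 125% | at 150% | at 200% |
|---|---|---|---|---|---|---|
| 56 | 336 | 252 | 370 | 420 | 504 | 672 |
| 84 | 504 | 378 | 554 | 630 | 756 | 1008 |
| 90 | 540 | 405 | 594 | 675 | 810 | 1080 |
| 100 | 600 | 450 | 660 | 750 | 900 | 1200 |

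Every count in the last four columns is non-compliant under protocol 6.4, and none is under the SAP. The result does not depend on the duration assumed.

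**The low side.** Taken literally, protocol 6.4 also makes 75% to just under 100% non-compliant. The SAP has therefore introduced a tolerance below 100% and no limit at all above it, and gives no reason for the asymmetry.

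**Pooling.** The ratio is taken over the whole exposure period, so opposite errors cancel. 42 days at double the tablets followed by 42 days at none gives 100 × (42 × 12 + 42 × 0) / 504 = 100%. No limit on this ratio, one-sided or two-sided, would detect that.

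**The case against.** The strongest reply is that the two definitions do different jobs. Protocol 6.4 governs what sites record. Read literally it would make 99% non-compliant, so it could not serve as a PP cut-off, and protocol 9.4.1 leaves the analysis sets to the SAP. That stands as a defence of having a tolerance. It does not explain why the tolerance is limited on one side only, or why Section 10 is silent.

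Several stronger readings are tempting, and the documents do not support them:

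- *Over-users necessarily stay in the PP set.* They might still be removed through the deviation route in SAP 6.5. Deviations are categorised under a management plan (SAP 8.2.2) that is not among the documents, and set membership is agreed before database lock (SAP 6.1).
- *Overuse is hidden.* SAP 8.1.1 lists all data and gives the maximum for continuous variables, so high values should be visible. They are just not counted as non-compliance.
- *High counts mostly reflect missing bottles.* Where bottles are lost or unreturned, compliance is set to missing. Only loose tablets absent from returned bottles could still inflate the ratio.
- *The PP analysis is the only look at actual intake.* Exposure-response modelling is planned under separate documents (SAP 7.1 and 7.2) and draws on measured exposure.
- *The dose groups are blurred.* Blinding uses two bottles with active and placebo tablets (protocol 6.1) and the strengths are redacted, so a high total count need not mean more active drug. Protocol 9.4.1 plans no comparison between dose levels.
- *The number of women can be estimated.* Assuming that 3% to 8% exceed 125% would give 0.03 × 380 = 11 to 0.08 × 380 = 30 women. The share has no source, and the base includes placebo and women who may not be in the PP set. Tablet supply per period is also redacted, so how easily such counts arise is unknown.

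**Conclusion.** The mismatch is real and small. The SAP's compliance classification and the PP compliance exclusion omit the upward direction that protocol 6.4 includes, and the departure is not declared. Counts above 100%, whatever their size, are neither tabulated as non-compliant nor excluded by the compliance criterion. Whether they could be excluded as deviations is left unstated.

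The number of women affected cannot be derived from the documents. The primary analysis uses the MFAS and is untouched; what is affected is one sensitivity analysis and one summary. The finding rests on the wording of the rules and on the SAP's formula, not on the assumed exposure. It does not show that the PP result will be biased or the dose comparison compromised.

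**What to change.** Before database lock, reconcile protocol 6.4 with SAP 6.5 and 8.2.6.2:

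- Make the SAP limit two-sided in both SAP sections. The upper cut-off is the sponsor's choice; above 125% would mirror the existing 75%. It is an analysis threshold only, is not taken from the documents, and says nothing about dosing or the management of overdose.
- Tabulate under-use and over-use separately by arm.
- State whether overuse counts as a critical or major deviation for the PP set.
- List the departure from protocol 6.4 in SAP Section 10. A two-sided tolerance still differs from the protocol's literal wording, so the entry is needed either way.

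The cost is a few sentences, no new data and a slightly smaller PP set. Because the ratio is pooled over the exposure period, over-use and under-use that cancel would still be missed.

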### 8.3. Analyses Supporting Primary Efficacy Objective

#### 8.3.1. Efficacy assessments

Participants will complete the efficacy assessments in the **CCI** eDiary in the order presented

below:

- Vaginal bleeding pattern
- Endometriosis-related pain NRS for OPP (including vaginal bleeding)
- Dyspareunia
- Interference with daily activities
- Rescue medication use and number of tablets
- Prohibited pain medication use and reason

HRQoL and Productivity Questionnaires are conducted at Study visits per SoA:

- PGI-S
- PGI-C
- EHP-30
- WPAI-Endometriosis
- PROMIS Fatigue Short Form 6a
- EQ-5D-5L

Participants will complete eDiary items **CCI** asking about the severity of their worst pain over the last 24 hours on 11-point NRS for endometriosis-related pain. Endometriosis-related pain severity will be provided based upon an NRS from 0 (no pain) to 10 (worst pain imaginable) where lower value represents a better outcome.

**CCI** DYS is defined as the NRS endometriosis-related pain severity entered on a menstrual bleeding day, and **CCI** NMPP is defined as the NRS endometriosis-related pain severity entered on a non-menstrual bleeding day. **CCI** OPP is defined as the NRS endometriosis-related pain severity entered on any day regardless of menstrual bleeding (i.e. one cycle of **CCI** OPP scores consists of **CCI** DYS scores and **CCI** NMPP scores for the cycle).

The definition for a menstrual bleeding day used in the determinations for **CCI** DYS and **CCI** NMPP will be based upon bleeding information collected from the **CCI** diary for the two questions below:

- (1a) During the past 24 h did you have any vaginal bleeding or spotting?

- (1b) During the past 24 h have you been on your period?

If both questions are answered “Yes”, then that day qualifies as a menstrual bleeding day and the pain score is DYS. If either question is answered “No”, then that day is a non-menstrual bleeding day and the pain score is NMPP. OPP score is defined as DYS for menstrual bleeding days and as NMPP for non-menstrual bleeding days.

### 8.3.2. Primary Efficacy Endpoint and Estimand

The primary efficacy endpoint is change from BC to TRC3 of the mean OPP score. The estimand is the mean difference between each OG-6219 dose arm and placebo in change from BC to TRC3 of the mean OPP score, assuming that all participants completed the treatment period, i.e. a hypothetical estimand. The estimand framework is described in Table 2.

### 8.3.3. Derivation of Primary Efficacy Endpoint

The mean OPP will be calculated for each cycle as the total of CCI pelvic pain scores reported during the cycle divided by the number of days during the cycle when a CCI score was reported. The mean OPP score will be calculated if there is at least one CCI pain score reported within that cycle.

#### 8.3.3.1. DEFINITION OF CYCLES

The definition of cycles for the calculation of averages over cycles are as follows:

- Screening cycle (SC) – starts at the start of menses associated with CCI and ends the day before the start of menses associated with CCI
- Baseline cycle (BC) – starts at the start of menses associated with CCI and ends at the day before the start of menses associated with CCI or the day of CCI whichever comes first.
- Treatment cycle 1 (TRC1) – starts at the day of CCI (randomization visit=day of first dose of randomized treatment) and ends the day before the start of menses associated with phone contact C (PC1).

- Treatment cycle 2 (TRC2) – starts at the start of menses associated with phone contact **C** and ends the day before the start of menses associated with **CCI**
- Treatment cycle 3 (TRC3) – starts at the start of menses associated with **CCI** and ends the day before the start of menses associated with **CCI** or, at the latest after **CCI** of randomized treatment.
- Safety follow-up cycle (SFC) – starts the day after the last dose of randomized treatment and ends 30 days after the last dose of randomized treatment.

Days after last dose of randomized treatment will only be included in SFC, and not in TRC1-TRC3.

#### 8.3.3.2. START OF MENSES

The primary source for determining start of menses dates is the eCRF. At each visit the first date of current menses/menstrual cycle was recorded in the eCRF. Since visits could be performed before the start of menses, the same first date of current menses could be recorded at two subsequent visits (if the next menses had not yet started when the visit was performed, the start date of the current menses was the same as at the previous visit). Therefore, the eCRF did not capture all start of menses days necessary to define the cycles.

To account for start of menses days not captured by the eCRF and correctly define the cycles, additional start of menses days could be identified using the information from the eCOA. The eCOA included the following two daily questions:

- 1a. During the past 24 h, did you have any vaginal bleeding or spotting?
- 1b. During the past 24h, have you been on your period?

If both questions were answered “yes”, the participant was regarded to have menses according to the eCOA.

Additional start of menses days were identified from the eCOA using the following algorithm:

- After randomization: If the participant had menses according to the eCOA in the time interval starting 15 days after the previous start of menses day recorded in the eCRF, and ending 4 days before the next start of menses day recorded in the eCRF

(the latter criteria only applies if there is a next start of menses recorded in the eCRF), the first day of menses according to the eCOA in that time interval was defined as an additional start of menses day for that participant.

- Before randomization: If the participant had menses according to the eCOA in the time interval starting 36 days before CCI and ending 4 days before CCI the first day of menses according to the eCOA in that time interval was defined as an additional start of menses day for that participant.

Additional start of menses days identified from the eCOA were added to the start of menses days in the eCRF only in cases where either a start of menses day in the eCRF was missing, or when a start of menses day in the eCRF was the same as the start of menses day recorded at the previous visit (for the start of menses associated with CCI also when it was the day before the start of menses day associated with CCI). If the start of menses day associated with CCI was missing, or recorded as the same as the start of menses associated with CCI (or before), the start of menses date associated with CCI was defined as the date of CCI.

#### 8.3.4. Intercurrent Event Handling and Data Imputation for Primary Efficacy Endpoint

See section 8.1.6, a hypothetical strategy will be used in the statistical analyses. If the mean score for TRC2 and/or TRC3 cannot be calculated, data will be assumed to be missing at random (MAR). No missing data will be imputed for the primary efficacy endpoint.

#### 8.3.5. Analysis of Primary Efficacy Endpoint

The primary endpoint will be analysed using a longitudinal model, i.e. a Mixed Models for Repeated Measures (MMRM), fitted to data from all participants with a post-treatment OPP measurement. The response vector for the model will be the change from BC in the mean OPP during TRC1, TRC2, and TRC3. Model terms will include the baseline cycle value (mean OPP for BC), treatment, time (i.e., cycle), and treatment-by-time interaction. An unstructured error structure will be assumed. If nonconvergence under the UN assumption is encountered a compound symmetry (CS) and autoregressive AR(1) error structures will be assumed in sequence. Estimated treatment differences (each OG-6219 treatment group versus

Placebo) with corresponding 95% CI and 2-sided p-values will be derived from the model for each treatment cycle.

Analysis using MMRM method will be implemented using the SAS® procedure MIXED as follows (example code only):

```
PROC MIXED DATA = ...;  
  CLASS CYCLE TREATMENT SUBJID;  
  MODEL CHG = BASELINE TREATMENT CYCLE TREATMENT*CYCLE /  
    DDFM=KR;  
  REPEATED CYCLE / SUBJECT = SUBJID TYPE=UN;  
  LSMEANS TREATMENT*CYCLE / PDIFF CL;  
RUN;
```

where CHG = change from baseline at each treatment cycle

TREATMENT = randomized treatment group (CCI BID, CCI BID, CCI BID, and placebo)

BASELINE = baseline cycle value

CYCLE = treatment cycle

SUBJID = subject ID

In addition, the mean OPP will be summarized by cycle and treatment group using descriptive statistics of observed data and change from baseline cycle values. Mean OPP by cycle will also be presented in listings.

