 - Note: Hormonal contraception is not permitted in the study. Women of childbearing potential must use adequate non-hormonal contraceptive methods to prevent pregnancy. Contraception must be used throughout the study starting at V1 through to CCI. The sporadic use of emergency contraception is permitted during the study. Refer to the Appendix 5 to review the non-hormonal contraceptives method for this study.
 - f) Not planning to relocate during the study (such that the participant would not be able to continue participation at the study site).
9. Must be willing and able to provide signed informed consent before any study-related activities.

At Visit C: Inclusion Eligibility Criteria:

10. Has moderate to severe ERP, determined by the NRS (0 to 10 anchored, with 0 [no pain] and 10 [extremely severe pain]), at CCI (before Randomization), based on the eDiary entries from the participant's last menstrual cycle (BC), as follows:
- a) An OPP (DYS and NMPP) CCI, OR
 - b) For DYS at least 2 days with CCI, OR CCI, OR
 - c) For DYS at least 2 days with CCI (not necessarily consecutive).
11. Has demonstrated compliance with CCI of eDiary entries (ie, pelvic pain score, vaginal bleeding, rescue medication intake) during both the SC and the BC.
- Note: eDiary compliance will be automatically calculated by the eDiary vendor portal and a report will be provided. The Investigational study site should review the report before the participant's schedule visit to assess eligibility at Randomization Visit CCI.
12. Is CCI compliant with the Placebo tablets over the BC (CCI), as determined by tablet accountability at the site.
13. Has taken only the study provided rescue medication, at a dose not exceeding the maximum dose determined by the Investigator, for control of ERP during the BC as evidenced in the eDiary.
- CCI
14. Have a negative pregnancy test as outlined in the SoA (Section 1.3).

* Please contact the Medical Monitor surrounding non-binary participants eligibility in the clinical study.

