#### 4.3. Sample Size

Approximately 760 pre-menopausal females aged 18 to 49 years old (inclusive), who have been surgically diagnosed with endometriosis within the last 4 months to 10 years prior to V1, will be screened to achieve 380 randomly assigned to the study treatment (95 participants in each group). A total of 380 participants will provide 84% power to detect a difference of 1 point between an OG-6219 dose group and Placebo in change from baseline to TRC3 of mean OPP, assuming a common SD of 2.2. This power calculation is based on a 2-sided test with Type I error of 0.05 and a dropout rate of 10%.

A minimum subset of 10 participants per group (~10%) will be enrolled for optional intensive PK sampling for the entire duration of the study.

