## 5. COVARIATES AND SUBGROUPS

### 5.1. Planned Covariates and Factors

The statistical analyses will include treatment, time, and treatment-by-time interaction as factors (if only one timepoint is included in the analysis, treatment will be the only factor). The baseline value of the endpoint will be included as a covariate (for endpoints where a baseline value exists).

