### 8.5. Analyses Supporting Exploratory Efficacy Objectives

#### 8.5.1. Exploratory Efficacy Endpoints

##### ENDOMETRIOSIS-RELATED PAIN (DYS, NMPP, OPP) SCORES

The exploratory efficacy endpoints for endometriosis-related pain scores are:

- Change from BC to TRC1 of the mean OPP score
- Change from BC to TRC1 of the mean DYS score

- Change from BC to TRC1 of the mean NMPP score
- Change from BC to TRC2 of the mean OPP score
- Change from BC to TRC2 of the mean DYS score
- Change from BC to TRC2 of the mean NMPP score
- Change from SC to SFC of the mean OPP score
- Change from SC to SFC of the mean DYS score
- Change from SC to SFC of the mean NMPP score

Change from SC to SFC of the score where means for a cycle will be calculated if there is at least one CCI score is reported within each of these cycles.

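### The primary MMRM does not use the Screening Cycle pain mean and forces one baseline slope across cycles; the estimate stays valid, but precision may be lost

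*SAP*

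**What the plan says.** The primary endpoint is change from BC to TRC3 in mean OPP, analysed by MMRM on the changes at TRC1, TRC2 and TRC3. SAP 8.3.5 states: "Model terms will include the baseline cycle value (mean OPP for BC), treatment, time (i.e., cycle), and treatment-by-time interaction". SAP Table 2 and Protocol 9.4.2 list the same terms, and SAP 5.1 gives the general rule: "The baseline value of the endpoint will be included as a covariate". The example SAS code contains neither an SC term nor a baseline-by-cycle term, so a single BC slope serves all three cycles. None of the sensitivity or supplementary analyses in SAP 8.3.6 and 8.3.7 adds either.

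SC pain scores are nevertheless collected under an eligibility rule. Protocol 5.1, criterion 11, sets a compliance threshold (redacted) for diary entries, which it specifies as "ie, pelvic pain score, vaginal bleeding, rescue medication intake) during both the SC and the BC". Footnote k of the Schedule of Activities repeats this as a condition of randomisation. SAP 8.3.3.1 defines the SC window, and SAP 8.5.1 lists an exploratory endpoint that needs the SC mean: "Change from SC to SFC of the mean OPP score".

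SAP 4.3 plans "95 participants in each group" and claims "84% power to detect a difference of 1 point", "assuming a common SD of 2.2", on a "2-sided test with Type I error of 0.05 and a dropout rate of 10" per cent.

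**The concern.** A second pre-randomisation pain mean is unaffected by treatment and probably predicts TRC3 pain. If it carries information beyond BC, omitting it makes the standard error of all three primary comparisons larger than the collected data require.

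The common slope is a separate restriction. If the BC mean predicts TRC1 better than TRC3, one slope fits neither cycle well. The estimand is hypothetical and relies on missing-at-random, so the model also stands in for TRC3 in women who stop early; an untested restriction on the baseline relation bears on that prediction too. Its effect through missing data has not been quantified here.

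**Working it through.** **1. The plan's own figure.** Inputs from SAP 4.3: 95 per arm, 10% dropout, difference 1, SD 2.2, two-sided alpha 0.05.
- Evaluable per arm: 95 × 0.9 = 85.5.
- SE = 2.2 × √(2/85.5) = 0.3365.
- Power = Φ(1/0.3365 − 1.96) = 84.4%. The stated 84% reproduces.

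**2. Gain from adding SC to a model that has BC.** The share of residual variance removed is the squared partial correlation of SC with TRC3 given BC. With S, B and T for SC, BC and TRC3:

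(r_ST − r_BT·r_SB)² / [(1 − r_BT²)(1 − r_SB²)]

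The documents give none of these correlations; every value below is an assumption.

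*All three equal to r.* The expression reduces to r²/(1+r)². Power takes 2.2 as the SD left after BC adjustment: Φ(1/(0.3365·√(1 − gain)) − 1.96).

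| r | Variance removed | Power, SC + BC |
|---|---|---|
| 0.2 | 2.8% | 85.4% |
| 0.4 | 8.2% | 87.3% |
| 0.5 | 11.1% | 88.3% |
| 0.6 | 14.1% | 89.4% |
| 0.7 | 17.0% | 90.3% |

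At 0.4 and 0.7 the SE falls by 4.2% and 8.9%. A simulation (86 per arm, 4,000 runs) gave variance reductions of 6.9% and 17.1% at those two values.

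*Correlation decaying with time.* SC is further from TRC3 than BC is.
- Pure AR(1): r_ST = r_BT·r_SB, so the gain is 0% at any correlation.
- Stable component (share 0.2 to 0.6) plus AR(1) decay (0.3 to 0.7 per cycle): 0.3% to 8.9%.
- One example, SC-BC 0.7, BC-TRC3 0.5, SC-TRC3 0.45: (0.45 − 0.35)²/(0.75 × 0.51) = 2.6%.

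**3. What the SD of 2.2 means.** SAP 4.3 does not say whether it is the raw SD of change or the SD after adjustment. If raw, with equal variances and a common correlation r, the BC-adjusted SD is 2.2·√((1+r)/2).
- r = 0.4: SD 1.84; power 94.4% with BC, 96.0% with SC added.
- r = 0.7: SD 2.03; power 89.7% with BC, 94.3% with SC added.

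**4. The common slope.** On the scale of the outcome (standardised, equal variances), the best BC slope at each cycle is its correlation with that cycle. If one slope b is used at TRC3, residual variance there rises by (r_BT − b)²/(1 − r_BT²).
- Equal correlations: b = r_BT, so the cost is zero.
- Assumed decay of the BC correlation, 0.7, 0.6, 0.5 at TRC1 to TRC3, with a common correlation of 0.6 to 0.8 between treatment cycles: the likelihood weights the slope by the inverse residual covariance, giving b = 0.632 to 0.667. The cost is 0.132²/0.75 = 2.3% to 0.167²/0.75 = 3.7%.

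Parts 2 and 4 therefore pull in opposite directions. The larger SC gain needs no decay, and then the slope terms gain nothing; with decay, the slope terms gain something and the SC gain shrinks. The two gains must not be added at their maxima.

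**The case against.** The strongest reply is that nothing here is an error. The endpoint is change from BC, adjusting for the endpoint's own baseline is the stated rule in both documents, the treatment contrast is valid without SC, and the stated power reproduces. Adding terms departs from the model in Protocol 9.4.2 for a gain nobody can yet size. All of that stands, and it makes this a suggestion about precision rather than a correction.

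The reply also rules out several stronger readings that a reader might infer:
- *That the plan forfeits 8-17% of residual variance as a matter of fact.* That range needs equal correlations of 0.4 to 0.7. SC precedes the single-blind placebo-tablet period in which BC is measured, so equal SC-TRC3 and BC-TRC3 correlation is not a neutral default. AR(1), with its zero gain, is one of the SAP's own fallback structures, although compound symmetry is tried before it.
- *That a complete Screening Cycle of scores exists for every woman.* The compliance threshold is redacted, and SAP 8.3.3 computes a cycle mean from as little as one score.
- *That BC is a poor covariate because women qualify on BC pain under criterion 10.* Selection on BC does not make it noisier, and any regression to the mean is shared with the randomised placebo arm. Nor does such selection remove the SC gain: under a linear normal model the partial correlation given BC is unchanged.

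A zero gain is also a special case: it needs pure AR(1) with cycle means free of measurement noise. A covariate need only precede randomisation and predict the outcome, so the different conditions in SC limit its value without disqualifying it.

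**Conclusion.** The point holds as a missed opportunity for precision. SC mean OPP is available before randomisation and already derived, yet it is absent from the primary model and from every sensitivity and supplementary analysis of the primary endpoint; the BC slope is held constant across cycles. The planned estimate is valid.

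The size rests wholly on assumed correlations: 8% to 17% of residual variance if SC, BC and TRC3 are equally correlated at 0.4 to 0.7, and about 0% to 9% under decay, where the baseline-by-cycle terms become the relevant part. A rise in power from 84% to at most about 87-90% further requires that 2.2 is the BC-adjusted SD; if it is the raw SD of change, the planned model already has about 90-94%. A reader might infer that the trial is underpowered without SC; the documents do not support that. The omission is certain, the gain is not.

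**What to change.** Before unblinding, amend SAP 5.1, Table 2 and 8.3.5 to add SC mean OPP as a second covariate, with BC*CYCLE and SC*CYCLE terms.

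State a rule for a missing SC mean. SAP 8.3.3.2 acknowledges that the eCRF did not capture every menses start date, and PROC MIXED would drop a woman with a missing covariate. Filling the covariate with the overall mean, blind to treatment, would keep everyone in the model.

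Apply the same terms to DYS, NMPP and rescue medication use. Include interference with daily activities only if it is confirmed to be recorded in SC: criterion 11 does not name it and the diary rows of the Schedule of Activities are redacted.

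Record the departure from the protocol's model terms in SAP section 10, which at present reports no changes to planned analyses.

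The SC-BC-TRC3 correlations can be estimated first from blinded pooled data, and the reason for adding or not adding the terms written down. The cost is SAP wording, that documented departure, and a few degrees of freedom against about 4 × 85.5 = 342 evaluable women. The endpoint, estimand and comparisons do not change.
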